6.2.2 Exclusion Criteria

The exclusion criteria are:

1. As per the Investigator (or designee) judgment, the subject cannot participate in the study for any reason (e.g., medical, psychiatric and/or social reason).
2. The subject is legally incompetent, physically or mentally incapable of giving consent (e.g., emergency situation, under guardianship, in a social or sanitary establishment, prisoner or involuntarily incarcerated).
3. Clinically relevant gastrointestinal, renal, hepatic, neurological, hematological, endocrine, oncological, urological, pulmonary, immunological, psychiatric or cardiovascular disorders or any other conditions that in the opinion of the investigators would jeopardize the safety of the participant or affect the validity of the study results.
4. Abnormal findings on physical examination, in the medical history, or in clinical laboratory results deemed clinically relevant by investigators (as per the common terminology criteria for adverse events [CTCAE]).
5. The subject has $(FEV_1/FVC) < 0.7$ and $FEV_1 < 80\%$ of the predicted value at post-bronchodilator spirometry.
6. The subject has asthma condition ($FEV_1/FVC < 0.75$ and reversibility in $FEV_1 > 12\%$ (or > 200 mL)) from pre- to post-bronchodilator values).
7. The subject has a body mass index (BMI) < 18.5 or ≥ 32 kg/m².
8. As per the Investigator's or designee's judgment, the subject has medical conditions which require or will require in the course of the study, a medical intervention (e.g., start of treatment, surgery, hospitalization) which may interfere with the study participation and/or study results.
9. The subject has used nicotine-containing products other than commercially available CC (either tobacco-based products or nicotine replacement therapies), as well as electronic cigarettes and similar devices after the Screening Visit, i.e., within 6 weeks prior to admission.
10. The subject has received medication (prescription or over-the-counter) in Table 2 of the protocol (except for vitamins) within 14 days or within 5 half-lives of the drug (whichever is longer) prior to Admission (Day -3) which has an impact on CYP1A2 or CYP2A6 activity.
11. The subject has a positive alcohol test and/or the subject has a history of alcohol abuse that could interfere with the subject's participation in the study.
13. The subject has a positive urine drug test.
14. The subject has positive serology test for human immunodeficiency virus (HIV)1/2, hepatitis B or hepatitis C.
15. The subject has donated or received whole blood or blood products within 3 months prior to Admission.

16. The subject is a current or former employee of the tobacco industry or their first-degree relatives (parent, sibling, child).
17. The subject is an employee of the investigational site or any other parties involved in the study or their first-degree relatives (parent, sibling and child).
18. The subject has participated in a clinical study within 3 months prior to the Screening Visit.
19. The subject has been previously screened in this study.
20. For women only: Subject is pregnant (does have positive pregnancy tests at the Screening and at Admission) or is breast feeding.
21. For women only: Subject does not agree to use an acceptable method of effective contraception.*

* Intrauterine device, intrauterine system, barrier methods of contraception (condoms, occlusive caps) with spermicidal foam/gel/film/suppository vasectomized partner(s), or true abstinence (periodic abstinence and withdrawal are not effective methods) from Screening until the end of the Safety Follow-up Period plus up to 3 days. Hysterectomy, tubal ligation, bilateral oophorectomy or post-menopausal status are reasons for not needing to use birth control. Post-menopausal status is defined as women who have not experienced menses for greater than 12 months. If a woman claims she's post-menopausal, but has had her menses within 12 months, a follicle stimulating hormone test must be performed and must be within acceptable limits.

6.3 Product Allocation and Blinding

6.3.1 Methods of Assigning Subjects to Product Arms

When all the eligibility criteria have been met, the subject will be enrolled on Day -3. Randomization will be done through [REDACTED] on Day -1 at any time during the day. Subjects will be randomized to one of the 2 study arms: CHTP 1.0:CC in a 1:1 ratio. Subjects will be informed of their randomized study arm in the morning of Day 1, prior to 06:30 AM (the start of the Exposure Period).

Stratified randomization will be conducted by sex and by average daily CC consumption over the last 6 weeks prior to Admission as self-reported (smokers smoking 10 to 19 CC/day and smokers smoking > 19 CC/day). In each arm, each sex and each of the smoking strata should have a quota applied to ensure they represent at least 40% of the population.

6.3.2 Blinding

This is an open-label study; therefore the subjects and Investigators or designees will be unblinded to the subject's arm. However, there will be a limited degree of blinding in the data review and data analysis process. In particular, PMI and contract research organization (CRO) personnel will be blinded to the randomized arm as summarized in Table 1.

**Table 1: Blinding Scheme**

Blinded Study Personnel	End of Blinding Period
PMI and CRO study statisticians	After the SAP finalization or database lock ¹ , whichever comes last.
PMI study data managers	After the finalization of PMI blind database review ² .
PMI clinical scientist	After the finalization of PMI blind database review ² . Can be actively un-blinded when appropriate.

¹ Data will be accessible blinded to randomization arm and to product use by means of a dummy randomization or masking.

² As part of the PMI quality control (QC) activity, data listings will be reviewed by the CRO and PMI before database lock, with no access to the randomization information. Full details will be available in the data review plan.

Any PMI and CRO personnel who are not listed in the above table will be unblinded by default.

6.3.3 Compliance to Product Allocation

Compliance for all study arms will be ensured by strict distribution of the products (stick by stick) and collection of the CC butts and CHTP 1.0 after each use. Distribution and return of these products will be documented in appropriate logs.

7 DERIVED AND COMPUTED VARIABLES

Mean change from baseline (baseline is defined in Section 12.1.4 “Definitions for Statistical Data Analysis”) is the mean of all individual subjects’ change from baseline values. Each individual change from baseline will be calculated by subtracting the individual subject’s baseline value from the value at the timepoint.

Mean percent change from baseline is the mean of all individual subjects’ percent change from baseline values. Each percent change from baseline will be calculated by subtracting the individual subject’s baseline value from the value at the desired timepoint and then

dividing this calculated value by the individual subject's baseline value and multiplying by 100.

When the baseline value is 0, 1 will be used in the denominator for calculating the percent change from baseline.

The QT interval corrected using Bazett's formula (QTcB) will be calculated as follows:

$$QTcB = \frac{QT}{\sqrt{\left(\frac{60}{HR}\right)}}$$

The QT interval corrected using Fridericia's formula (QTcF) will be calculated as follows:

$$QTcF = \frac{QT}{\sqrt[3]{\left(\frac{60}{HR}\right)}}$$

Reported BMI will be calculated at site from the body weight and height using the following formula:

$$BMI = \frac{\text{weight in kilograms}}{\text{height in meters}^2} \quad (\text{kg/m}^2)$$

7.1 Biomarkers

7.1.1 Biomarkers of Exposure

The adjustment of the urinary BoExp concentration for creatinine will be calculated as:

$$\text{Biomarker (corrected for creatinine)} = \frac{[\text{Biomarker}]}{[\text{Creatinine}]}$$

where the [] indicated concentrations measured from the same 24 hour urine collection.

The quantity excreted for a BoExp over 24 hours will be calculated as:

$$\text{Quantity Excreted over 24 hours} = [\text{Biomarker}] * \text{urine volume}$$

where the concentration and the urine volume are from the same 24 hour urine collection.

7.1.2 Nicotine Equivalents

The quantity excreted of NEQ over 24 hours will be derived according to the formula below. The concentrations reported for free nicotine and its five major metabolites will not be used as analysis variables.

$$\begin{aligned} \text{NEQ [g]} &= (\text{free nicotine}_c [\mu\text{mol/L}] + \text{nicotine-glucuronide}_c [\mu\text{mol/L}] \\ &+ \text{free cotinine}_c [\mu\text{mol/L}] + \text{cotinine-glucuronide}_c [\mu\text{mol/L}] \\ &+ \text{free trans-3'-hydroxycotinine}_c [\mu\text{mol/L}] \\ &+ \text{trans-3'-ydroxycotinine-glucuronide}_c [\mu\text{mol/L}]) \\ &*162.2[\mu\text{g}/\mu\text{mol}]*\text{urine volume (L)} / 1000 [\mu\text{g}/\text{mg}] \end{aligned}$$

N.B. All concentrations must be in $\mu\text{mol/L}$ before applying the above formula.

The conversion factors will be applied as follows:

Free nicotine	The molecular weight is 162.232 g/mol (Chemical Information Specialized Information Services RN:54-11-5). Therefore to convert nicotine from ng/mL to nmol/L, the result in ng/mL is multiplied by 6.164.
Nicotine glucuronide	The molecular weight is 338.356 g/mol (Chemical Information Specialized Information Services RN:152306-59-7). Therefore to convert nicotine from ng/mL to nmol/L, the result in ng/mL is multiplied by 2.955.
Cotinine	The molecular weight is 176.218 g/mol (Chemical Information Specialized Information Services RN:486-56-6). Therefore to transform cotinine from ng/mL to nmol/L, the result in ng/mL will be multiplied by 5.675.
Cotinine-glucuronide	The molecular weight is 352.341 g/mol (Chemical Information Specialized Information Services RN:139427-57-9). Therefore to transform cotinine from ng/mL to nmol/L, the result in ng/mL will be multiplied by 2.838.
Trans-3'hydroxycotinine	The molecular weight is 192.217 g/mol (Chemical Information Specialized Information Services RN:34834-67-8). Therefore to transform trans-3' hydroxycotinine from ng/mL to nmol/L, the result in ng/mL is multiplied by 5.202.
Trans-3'hydroxycotinine-glucuronide	The molecular weight is 368.34 g/mol (Chemical Information Specialized Information Services RN:132929-88-5). Therefore to transform trans-3' hydroxycotinine from ng/mL to nmol/L, the result in ng/mL is multiplied by 2.715.

The adjustment of NEQ for creatinine in urine will be calculated as:

$$\text{NEQ (corrected for creatinine)} = \frac{[\text{NEQ}]}{[\text{Creatinine}]}$$

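### SAP 7.1.2 gives inconsistent units for nicotine equivalents: the formula yields mg but is labelled g, and the listed factors give nmol/L where it needs µmol/L, so absolute NEQ levels could be wrong by 1000-fold

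*SAP*

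**What the plan says.** SAP 7.1.2 gives one formula for NEQ, for the amount excreted over 24 hours. The result and the first of six inputs are printed as "NEQ [g]} &= (\text{free nicotine}_c [\mu\text{mol/L". The remaining inputs carry the same µmol/L unit, and their sum is scaled by "162.2[\mu\text{g}/\mu\text{mol}]*\text{urine volume (L)} / 1000 [\mu\text{g}/\text{mg". A note beneath says "N.B. All concentrations must be in $\mu\text{mol/L}$ before applying the above formula".

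A list of molecular weights and conversion factors follows. For free nicotine it reads "Therefore to convert nicotine from ng/mL to nmol/L, the result in ng/mL is multiplied by 6.164", and for cotinine "Therefore to transform cotinine from ng/mL to nmol/L, the result in ng/mL will be multiplied by 5.675". The other four analytes are given for the same pair of units, ng/mL to nmol/L.

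The section closes with "The adjustment of NEQ for creatinine in urine will be calculated as" and the ratio [NEQ] over [Creatinine]. SAP 7.1.1 uses the same ratio for the other urinary biomarkers and explains that the brackets "indicated concentrations measured from the same 24 hour urine collection". Secondary objective 3 in SAP 5.2 asks for NEQ both as an amount and as a creatinine-adjusted concentration.

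**The concern.** A derivation section is what the programmer codes from, and this one disagrees with itself twice. The unit on the left of the formula is not the unit its terms produce. The unit that the conversion list produces is not the unit the formula takes in. Each mismatch is a factor of exactly 1000.

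Secondary objective 3 is about nicotine levels, so the absolute value matters here and not only the comparison between arms. Under SAP 12.5.2.1.2, NEQ levels go into descriptive Table 15.2.4.14, Figures 15.1.2.27 and 15.1.2.28, and back-transformed least-squares means. The cotinine and trans-3'-hydroxycotinine factors also appear in SAP 7.1.4 for the CYP2A6 ratio, where a common scale cancels. It does not cancel in a 24-hour amount.

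**Working it through.** **1. Output unit.** Taking the units from the formula in SAP 7.1.2:

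(µmol/L) × (µg/µmol) × L ÷ (µg/mg) = mg

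The stated unit, g, is not reproduced. The formula's own divisor of 1000 µg per mg leads to milligrams.

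**2. Conversion factors.** A concentration in ng/mL (equal to µg/L) times 1000, divided by the molecular weight, gives nmol/L. Using the molecular weights in SAP 7.1.2:

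| Analyte | Molecular weight | 1000/MW | SAP factor | Factor for µmol/L |
|---|---|---|---|---|
| Free nicotine | 162.232 | 6.1640 | 6.164 | 0.006164 |
| Nicotine-glucuronide | 338.356 | 2.9555 | 2.955 | 0.002955 |
| Cotinine | 176.218 | 5.6748 | 5.675 | 0.005675 |
| Cotinine-glucuronide | 352.341 | 2.8382 | 2.838 | 0.002838 |
| Trans-3'-hydroxycotinine | 192.217 | 5.2025 | 5.202 | 0.005202 |
| Trans-3'-hydroxycotinine-glucuronide | 368.34 | 2.7149 | 2.715 | 0.002715 |

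All six SAP factors agree with 1000/MW to within 0.001. They are right for nmol/L and 1000 times too large for µmol/L.

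**3. Size, on assumed values.** The documents give no NEQ levels. Assume 1000 ng/mL of each analyte and 1.5 L of urine.

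- Sum with the SAP factors: 1000 × (6.164 + 2.955 + 5.675 + 2.838 + 5.202 + 2.715) = 25,549 nmol/L = 25.549 µmol/L.
- Correct amount: 25.549 × 162.2 × 1.5 / 1000 = 6.216 mg, or 0.006216 g.
- Correct number read with the printed label: 6.216 g, 1000 times too high.
- nmol/L entered without the extra division: 25,549 × 162.2 × 1.5 / 1000 = 6216.1, again 1000 times too high.
- Both slips together: 6216.1 read as g against 0.006216 g, a factor of 1,000,000.

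**4. Effect on comparisons.** SAP 12.5.2.1.2 analyses NEQ on the log scale and reports 100% minus the ratio of arms. Since log(1000x) = log 1000 + log x, a uniform error adds the same constant to every observation in both arms and drops out of the difference. A simulated check with 40 values per arm gave a geometric mean ratio of 0.882 before and after multiplying by 1000. Percent change from baseline is (1000x − 1000b)/(1000b) = (x − b)/b, also unchanged.

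**5. Creatinine ratio.** SAP 7.1.1 makes the bracketed quantity a concentration. For NEQ this is the printed formula without its volume term: molar sum × 162.2 / 1000. In the example, 25.549 × 162.2 / 1000 = 4.144 mg/L. SAP 7.1.2 does not write this step.

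**The case against.** Three points stand in the plan's favour.

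- The note requiring µmol/L tells the programmer what the formula needs, and the factors are openly labelled nmol/L. Someone who follows both must divide by 1000. This makes a wrong value less likely, but the step is still unwritten, and the list placed directly after the note delivers a different unit.
- The g may be a reading artefact. The same formula has lost a letter in the name of its last analyte, so a lost m in mg is possible. The output-label point therefore needs a look at the signed PDF. The nmol/L against µmol/L mismatch does not depend on it.
- The consequences are narrow. NEQ is secondary, has no multiplicity control (SAP 12.1.7), has no cut-off among the categorical variables in SAP 7.4, and is not among the topline or registry tables in SAP 13.3 and 13.5.

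A reader might also infer that the creatinine-adjusted NEQ will be computed from the 24-hour amount, because that is the only NEQ formula printed. The documents do not support this. The brackets in SAP 7.1.1 mean concentration, SAP 5.2 asks for a creatinine-adjusted concentration, and SAP 12.5.2.1.2 analyses creatinine-corrected concentrations. The intended quantity can be worked out, so what is missing is a line of clarification. Even if it were misread, the adjusted value would be multiplied by urine volume in litres (1.0 to 2.5-fold over an assumed 1.0 to 2.5 L), so this point adds nothing to the 1000-fold error.

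**Conclusion.** SAP 7.1.2 is inconsistent in its units as printed. The formula yields mg against a label of g, subject to the PDF caveat. The listed factors yield nmol/L against a required µmol/L, with no division by 1000 written. Absolute NEQ levels could be mislabelled or wrong by 1000-fold, or by 1,000,000-fold if both slips occur together.

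It would be tempting to conclude that the nicotine comparison between arms is unreliable. That does not follow. If the error is applied uniformly, which is what coding one rule for all subjects would do, the ratio, the percent reduction and the percent change from baseline are all unchanged. The primary biomarkers use a different derivation. Nor do the documents show that a wrong value will be produced, since the note on µmol/L guards partly against it. The point is a derivation rule that needs correcting for a secondary endpoint about levels.

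**What to change.** In SAP 7.1.2:

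- Label the result mg per 24 hours, after checking the signed PDF for the printed unit.
- Restate the six factors as ng/mL to µmol/L (last column of the table above), or keep them and add an explicit division by 1000 before the formula.
- As a clarification, state that [NEQ] in the creatinine ratio is the molar sum in µmol/L × 162.2 / 1000, in mg/L, without urine volume.

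The cost is SAP wording and the derived-variable specification. No new data, design change or change to the statistical model is involved.

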7.1.3 CYP1A2

CYP1A2 activity is calculated as the molar metabolic ratio of PX / CAF in plasma, both expressed in molar equivalent (nmol/L).

The conversion factor will be applied as follows:

PX	The molecular weight is 180.166 g/mol (Chemical Information Specialized Information Services RN:611-59-6). Therefore to convert PX in ng/mL to nmol/L the result in ng/mL is multiplied by 5.550.
CAF	The molecular weight is 194.193 g/mol. (Chemical Information Specialized Information Services RN:58-08-2). Therefore to convert CAF in ng/mL to nmol/L the result in ng/mL is multiplied by 5.150.

The converted results will be calculated to three decimal places and the ratio will be reported as a percentage with two decimal places.

If either of the PX or CAF concentration is LLOQ then the ratio will not be calculated.

7.1.4 CYP2A6

CYP2A6 activity is calculated in plasma as the metabolic ratio of trans-3' hydroxycotinine to cotinine, both expressed in molar equivalent (nmol/L) (**Jacob et al. 2011**).

The conversion factor will be applied as follows:

Cotinine	The molecular weight is 176.215 g/mol (Chemical Information Specialized Information Services RN:486-56-6). Therefore to transform cotinine from ng/mL to nmol/L, the result in ng/mL will be multiplied by 5.675.
Trans-3'hydroxycotinine	The molecular weight is 192.217 g/mol (Chemical Information Specialized Information Services RN:34834-67-8). Therefore to transform trans-3' hydroxycotinine from ng/mL to nmol/L, the result in ng/mL is multiplied by 5.202.

The converted results will be calculated to three decimal places and the ratio will be reported as a percentage with two decimal places.

If either of the cotinine or trans-3'hydroxycotinine concentration is LLOQ then the ratio will not be calculated.

7.2 Questionnaires

All used questionnaires are available as a validated questionnaire in Polish.

7.2.1 Fagerström Test for Nicotine Dependence (FTND)

The FTND will be used in its revised version (**Heatherton et al 1991**), as updated in 2012 (**Fagerström et al. 2012**). These questions are to be answered by the subject themselves. It is conducted at Screening only to determine subject's dependence on nicotine.

Table 2 describes the six questions the questionnaire consists of, and the scores associated with each question.

The FTND total score will be derived by summing the individual item scores if all items are non-missing, otherwise the total score will be set to missing. For the FTND total score, descriptive statistics and frequency tables according to the following classification will be provided (**Fagerström et al. 2012**):

Mild 0 – 3

Moderate 4 – 6

Severe 7 – 10

**Table 2: Scoring for the Fagerstrom Test for Nicotine Dependence**

	FTND Question	Response	Score
1	How soon after you wake up do you smoke your first cigarette?	
▪ Within 5 minutes▪ 6 to 30 minutes▪ 31 to 60 minutes▪ After 60 minutes	
3210
2	Do you find it difficult to refrain from smoking in places where it is forbidden?	
▪ Yes▪ No	
10
3	Which cigarette would you hate most to give up?	
▪ The first one in the morning▪ Any other	
10
4	How many cigarettes per day do you typically smoke?	
▪ 10 or less (up to ½ pack)▪ 11 to 20 (a little more than ½ pack, up to a full pack)▪ 21 to 30 (a little more than a pack, up to 1½ packs)▪ 31 or more (more than 1½ packs)	
0123
5	Do you smoke more frequently during the first hours after waking than during the rest of the day?	
▪ Yes▪ No	
10
6	Do you smoke if you are so ill that you are in bed most of the day?	
▪ Yes▪ No	
10

7.2.2 Questionnaire of Smoking Urges-Brief (QSU-brief)

The QSU-brief (Cox et al. 2001) is a self-reported questionnaire completed daily from Day -2 to Day 5 between 08:00 PM and 11:00 PM.

The QSU-brief consists of 10 items as presented in **Table 3**.

**Table 3: Questionnaire of Smoking Urges Brief - Questions and Factors**

	Question	Factor
1	I have a desire for a cigarette right now	1
2	Nothing would be better than smoking a cigarette right now	2
3	If it were possible, I probably would smoke now	1
4	I could control things better right now if I could smoke	2
5	All I want right now is a cigarette	2
6	I have an urge for a cigarette	1
7	A cigarette would taste good now	1
8	I would do almost anything for a cigarette now	2
9	Smoking would make me less depressed	2
10	I am going to smoke as soon as possible	1

All items will be rated on a 7-point scale, ranging from 1 (strongly disagree) to 7 (strongly agree). Higher scores indicate a higher urge to smoke.

Two factor scores and a total score will also be derived (Cox et al. 2001). Each factor is a subset that includes 5 of the 10 questions as defined in **Table 3**. Factor 1 represents the desire and intention to smoke with smoking perceived as rewarding, while Factor 2 represents an anticipation of relief from negative effect with an urgent desire to smoke.

The factors and total scores will be calculated by averaging non-missing item scores if at least 50% are non-missing, otherwise the factor or total score will be set to missing.

7.2.3 Modified Cigarette Evaluation Questionnaire

The MCEQ (Cappelleri et al. 2007) will be completed by the subject him/herself daily from Day -2 to Day 5 between 08:00 PM and 11:00 PM, to assess the degree to which subjects experience the reinforcing effects of smoking.

The MCEQ consists of 12 items as presented in **Table 4**.

**Table 4: Modified Cigarette Evaluation Questionnaire - Questions and Subscales**

	Question	Subscale
1	Was smoking satisfying?	Smoking Satisfaction
2	Did cigarettes taste good?	Smoking Satisfaction
3	Did you enjoy the sensation in your throat and chest?	Enjoyment of Respiratory Tract Sensations
4	Did smoking calm you down?	Psychological Reward
5	Did smoking make you feel more aware?	Psychological Reward
6	Did smoking make you feel less irritable?	Psychological Reward
7	Did smoking help you concentrate?	Psychological Reward
8	Did smoking reduce your hunger for food?	Psychological Reward
9	Did smoking make you dizzy?	Aversion
10	Did smoking make you nauseous?	Aversion
11	Did smoking immediately relieve your craving for a cigarette?	Craving Reduction
12	Did you enjoy smoking?	Smoking Satisfaction

Items are assessed on a 7-point scale, ranging from 1 (not at all) to 7 (extremely). Higher scores indicate greater intensity on that scale.

The subscales scores will be derived by averaging the individual non-missing item scores if at least 50% are non-missing, otherwise the subscale score will be set to missing.

